8.3.5 ADVERSE EVENT REPORTING

We will be adopting the following reporting procedures:

| What event is reported | When is event reported | By whom is event reported | To whom is event reported |
|---|---|----------------------------------|--|
| Fatal or life-threatening unexpected, suspected serious adverse reactions | Within 24 hours of initial receipt of information | Investigator | 
 Local/internal IRB |
| Non-fatal, non-life-threatening unexpected, suspected serious adverse reactions | Within 48 hours of initial receipt of information | Research Personnel | 
 Local/internal IRB |
| Unanticipated adverse device effects | Within 10 working days of investigator first learning of effect | Investigator | 
 Local/internal IRB |
| Unanticipated Problem that is not an SAE | Within 7 days of the investigator becoming aware of the problem | Investigator | 
 Local/internal IRB |

8.3.6 REPORTING OF PREGNANCY

There have been some scientific studies using transcranial electrical stimulation in pregnancy (see (Kurzeck, Kirsch et al. 2018) and (Konstantinou, Vigod et al. 2020) for review). None of these studies reported side-effects specific to pregnancy or fetal development. Furthermore, given the history of an extremely safe profile for non-invasive electrical stimulation with zero serious adverse events after decades of use, we assume there to be no risk to pregnant women. Nonetheless, pregnant women will be excluded from this study because they are a protected group. Female participants will be asked if there is a possibility that they are pregnant at both sessions. If the participant says yes or is unsure, then we will verify pregnancy status via a urine pregnancy test. Only upon a verbal confirmation that pregnancy is not possible or a negative finding from a pregnancy test will we proceed with the experiment.

8.4 UNANTICIPATED PROBLEMS

8.4.1 DEFINITION OF UNANTICIPATED PROBLEMS (UP)

The Office for Human Research Protections (OHRP) considers unanticipated problems involving risks to participants or others to include, in general, any incident, experience, or outcome that meets **all** of the following criteria:

- Unexpected in terms of nature, severity, or frequency given (a) the research procedures that are described in the protocol-related documents, such as the Institutional Review Board (IRB)-approved research protocol and informed consent document; and (b) the characteristics of the participant population being studied;
- Related or possibly related to participation in the research (reasonable possibility that the incident, experience, or outcome may have been caused by the procedures involved in the research); and
- Suggests that the research places participants or others at a greater risk of harm (including physical, psychological, economic, or social harm) than was previously known or recognized.

8.4.2 UNANTICIPATED PROBLEM REPORTING

If a UE occurs, the IRB will be notified, and the study will be adjusted as needed to protect the health and safety of the participants. Depending on the nature of the UE, the research protocol, inclusion/exclusion criteria, and informed consent will be changed to reflect the possibility of this event reoccurring. During this time, no new participants will be recruited and the research procedures for currently enrolled participants will be stopped. Each UE will be recorded and reported throughout the study.

8.4.3 REPORTING UNANTICIPATED PROBLEMS TO PARTICIPANTS

Any new information gained during the study that may affect a participant's willingness to continue in the study will be reported to all currently enrolled participant.

9. STATISTICAL CONSIDERATIONS

Statistical analyses will be performed by [name].

9.1 STATISTICAL HYPOTHESES

- Primary Outcome hypothesis:
 - Null: There is no difference in goal-directed behavior between baseline EEFRT and EEFRT during stimulation as a function of stimulation type (delta-beta tACS, theta-gamma tACS, or active-sham).
 - Alternate: There is a difference in goal-directed behavior between baseline EEFRT and EEFRT during stimulation as a function of stimulation type (delta-beta tACS, theta-gamma tACS, or active-sham).
- Secondary Outcome hypothesis:
 - Null: There is no difference in delta-beta phase-amplitude coupling strength between prefrontal electrodes and left motor electrodes for post-stimulation resting-state periods as a function of stimulation type (delta-beta tACS, theta-gamma tACS, or active-sham).

- Alternate: There is a difference in delta-beta phase-amplitude coupling strength between prefrontal electrodes and left motor electrodes for post-stimulation resting-state periods as a function of stimulation type (delta-beta tACS, theta-gamma tACS, or active-sham).
- Exploratory Outcome hypothesis 1:
 - Null: The impact of delta-beta tACS on goal-directed behavior is not correlated with motivation symptom severity.
 - Alternative: The impact of delta-beta tACS on goal-directed behavior is correlated with motivation symptom severity.
- Exploratory Outcome hypothesis 2:
 - Null: Functional connectivity during the resting-state between dorsal striatum and lateral prefrontal cortex is not predictive of the impact of delta-beta tACS on goal-directed behavior.
 - Alternative: Functional connectivity during the resting-state between dorsal striatum and lateral prefrontal cortex is predictive of the impact of delta-beta tACS on goal-directed behavior.

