3. OBJECTIVE AND OUTCOME MEASURES

| OBJECTIVES | OUTCOMES | JUSTIFICATION FOR OUTCOMES |
|--|---|--|
| Primary | | |
| To investigate whether delta-beta tACS will produce an increase in goal-directed behavior during reward-based decision-making. | Behavioral metric, percentage of hard trials chosen, during the Expenditure of Effort for Reward Task (EEfRT) at Session 1. | Stimulation is delivered during task performance and the amount of time on task with stimulation was sufficient to observe meaningful changes in goal-directed behavior across participants in our previous study. |
| Secondary | | |

| OBJECTIVES | OUTCOMES | JUSTIFICATION FOR OUTCOMES |
|--|--|---|
| To investigate whether delta-beta tACS will result in a lasting increase in delta-beta coupling during eyes-open resting-state recorded immediately following stimulation | Neural metric, degree of phase-amplitude coupling between prefrontal delta oscillations and left motor beta oscillations, quantified during eyes-open resting-state recorded post-stimulation intermittent with task blocks. | Our previous study delivering stimulation in the same manner with intermittent resting-state EEG found evidence of increased phase-amplitude coupling from stimulation. |
| Exploratory | | |
| To investigate the degree to which motivation symptoms predict individual differences in the impact of delta-beta tACS on performance. | Two-dimension factor analysis is run on clinical assessments to derive a motivation symptoms and mood symptoms dimension. These scores are correlated with the impact of tACS on behavior. | Our previous study found two symptom dimensions within participants with major depressive disorder that captured individual differences in reward-based decision-making. |
| To investigate whether rewarding learning might be impaired in addition to goal-directed behavior in participants with MDD and anhedonia. | Optimal decision-making for rewarding stimulus is predicted to be impaired as a function of anhedonia and may be improved with delta-beta tACS. | Previous literature suggests that reward-learning is impaired in patients with depression and symptoms of anhedonia. This additional task allows for the investigation of the specificity of tACS to influence a specific reward-based cognitive process. |

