9.2 SAMPLE SIZE DETERMINATION

The sample size is 48 participants in the final dataset to be used in analysis. However, to ensure that 48 participants complete the experiment, we conservatively estimate to enroll 100 participants as a ceiling for the sake of IRB approval. The motivation for the sample size of 48 participants in the analysis is explained below. The sample size is determined based on previous experiments from our group: the effect size of previous findings and the reliability of our estimates. Our estimators are precise due to sufficient number of trials per condition with each participant and that the tasks are titrated to the individual.

Primary outcome: Cross-frequency transcranial alternating current stimulation (tACS) to lateral frontal cortex at delta-beta frequency will increase goal-directed behavior relative to placebo stimulation.

Previous Data: The planning and refinement of the proposed study was informed by our previous experiments that serve as preliminary data for the proposal. In our previous experiment, we delivered cross-frequency tACS to lateral frontal cortex at delta-beta frequency to modulate performance on a cognitive control task relative to placebo stimulation (Riddle, McFerren et al. 2021). As in the current proposal, a specific component of the task was identified to drive an increase in delta-beta coupling. This was the component that was altered by delta-beta tACS. In the previous experiment, we found a significant interaction between stimulation (delta-beta tACS or theta-gamma tACS, minus placebo) and our cognitive control dimension of interest with a partial-eta square of 0.288 with $N = 23$. For the specific comparison of interest, we found increased reaction time relative to placebo with an effect size of 0.480 from pair-wise t-test with $N = 23$.

Sample Size Determination and Power Calculation: Our previous effect size based on behavioral modulation from delta-beta tACS used a crossover design. The experiment proposed here will use a parallel arm design; however, we will calculate the effect of stimulation as a difference from the baseline

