performance levels that are derived from our titration of task difficulty. Therefore, the primary analysis will use a mixed-measures ANOVA with one within-participants factor (before and during stimulation) and one between-participants factor (delta-beta, placebo). With an effect size of 0.288 partial-eta square, we estimate that we need at least 21 participants to reach 80% statistical power with a correlation of 0.7. Using a conservative estimate of 0.5 correlation between estimates, we still reach 93% statistical power with 48 participants.

[figure not shown]

Figure 3. Power calculation for the impact of delta-beta tACS on performance tested with ANOVA: between-participants factor of stimulation type and within-participants factors before versus after stimulation. Interaction effect was modeled as a within-between ANOVA using the G*Power software: 3 groups, 2 measurements, partial-eta square 0.288, correlation between estimates conservatively at 0.5. Proposed number of participants, 48, is depicted in red.

Data will be collected until we reach 48 participants. Given the similarity in stimulation methodology between the current experiment and our previous experiment (Riddle, McFerren et al. 2021), we anticipate adequate levels of power for hypothesis testing with 48 total participants.

Secondary outcome: Cross-frequency transcranial alternating current stimulation (tACS) to lateral frontal cortex at delta-beta frequency will increase delta-beta coupling relative to placebo stimulation.

Previous Data: The planning and refinement of the proposed study was informed by our previous experiment that serves as preliminary data for the proposal. In our previous experiment, we delivered cross-frequency tACS to lateral frontal cortex at delta-beta frequency to modulate performance on a cognitive control task relative to placebo stimulation (Riddle, McFerren et al. 2021). As in the current proposal, resting-state EEG sessions were included between each task block such that phase amplitude coupling could be estimated with data that was not corrupted by the stimulation artifact from tACS. In

the previous experiment, we found that delta-beta tACS increased delta-beta coupling with an effect size of 0.382 and a sample size of 23 participants.

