9.4 STATISTICAL ANALYSES

9.4.1 GENERAL APPROACH

All testing described below assumes a significance threshold of $p = 0.05$. Analyses will be deemed to be statistically significant if the p -value is less than this threshold. An analysis that does not exceed this threshold will be considered inconclusive. Continuous data will be described using means, standard deviations, and confidence intervals, while categorical data will be described using counts/percentages.

There may be additional covariates included in the analysis. Data will be assessed for normality and, if deemed necessary, corrective procedures will be applied (e.g., log normalization). Based on our previous dataset, we expect that the variables used here will be approximately Gaussian. However, if the distribution of a variable displays a skewed tail and a test for normality fails, then it is justified to use a corrective procedure. This correction will be applied upon consideration of the variables themselves, and not based on the result of the intended analysis.

Data will be collected until 48 participants complete the first session and all data is usable. Given that there is only a single session, we expect to have complete data and all analyses will include the full participant pool. However, if there are technical errors that are not caught in time, then the affected analyses may have less participants. In this scenario, the data for a participant is then completely removed from the analysis. We emphasize that lost data is typically of greater concern for longitudinal and multi-session studies. If a subset of participants does not complete the second session in this experiment, then only the analysis of exploratory outcome 2 will be affected.

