9.4.2 ANALYSIS OF THE PRIMARY OUTCOME (BEHAVIOR)

Goal-directed behavior will be calculated as the average decision to perform the HARD task. The average for the four blocks prior to stimulation and the four blocks during stimulation will be calculated. A two-way analysis of covariance (ANCOVA) will be performed using within-participant factor of time (before or during stimulation), between-participant factor stimulation type (delta-beta tACS, theta-gamma tACS, or active-sham), and anhedonia symptom severity as a linear covariate (SHAPS at session 1 as a continuous variable). We hypothesize to find an interaction between time and stimulation type in the ANCOVA. Post-hoc differences will be investigated using Tukey's test. We hypothesize that the predicted interaction will be driven by an increase in goal-directed behavior for delta-

beta tACS. Sensitivity analyses will be conducted to evaluate the specificity of these effects: a similar analysis with reward-evaluation as the dependent variable and we do not expect that delta-beta tACS will have any effect on reward-evaluation.

Furthermore, we hypothesize that the inclusion of the SHAPS covariate is critical to our findings in that participants with the greatest symptoms of anhedonia will demonstrate the greatest increase to goal-directed behavior. This effect will be investigated by a correlation between the baseline symptoms of anhedonia (SHAPS) and the change in goal-directed behavior for participants that received delta-beta tACS. The specificity of this effect will be investigated as a difference in correlation between the relationship of anhedonia symptoms and goal-directed behavior for the group that received sham tACS.

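### The formal primary test is an undirected three-arm interaction, so it can be positive without answering the delta-beta objective, and section 9.2 describes a different, two-level primary analysis

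*Combined protocol and SAP*

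**What the plan says.** The objective in section 3, repeated in the synopsis (1.1), is directional and concerns one arm: "To investigate whether delta-beta tACS will produce an increase in goal-directed behavior during reward-based decision-making". Neither place names a comparator. Section 9.2 does, wording the primary outcome as tACS that "at delta-beta frequency will increase goal-directed behavior relative to placebo stimulation".

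The formal alternative in 9.1 is wider: "There is a difference in goal-directed behavior between baseline EEFRT and EEFRT during stimulation as a function of stimulation type", with delta-beta, theta-gamma and active sham listed as the types. Section 9.4.2 fits this with "between-participant factor stimulation type (delta-beta tACS, theta-gamma tACS, or active-sham), and anhedonia symptom severity as a linear covariate" and looks to the time-by-stimulation interaction. It then says "Post-hoc differences will be investigated using Tukey's test". The direction appears only as an expectation: "We hypothesize that the predicted interaction will be driven by an increase in goal-directed behavior for delta" (the quotation stops at a line-break hyphen; the sentence goes on to name delta-beta tACS). Section 9.4.1 sets the threshold, "All testing described below assumes a significance threshold of $p = 0.05", and no section says which comparison must be significant for the objective to be met.

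The text of 9.2 describes the primary analysis differently, with "one between-participants factor (delta-beta, placebo" as its two levels. The caption of Figure 3 in the same section models three groups. The secondary outcome repeats the pattern: two levels in the 9.2 text, three in 9.1, 9.4.3 and Figure 4.

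**The concern.** The three-arm interaction null is false whenever any arm's change differs from the others. That includes a trial in which theta-gamma moves behaviour and delta-beta does nothing, and one in which delta-beta lowers it. In both, the hypothesis labelled primary would be reported as supported while the objective is not met. A theta-gamma effect is not fanciful: section 4.2 reports that both waveforms modulated behaviour tied to their targeted activity in the group's earlier study, although in a different task.

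The second cost is power. No objective asks about theta-gamma versus sham, yet the comparison that answers the objective shares its error rate with that pair under Tukey.

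Third, the primary test is not fixed. A two-group ANOVA, a three-group interaction and a Tukey pair can each be defended from the text after the data are seen.

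**Working it through.** **Inputs.** Three arms, 48 participants, 8 in each of 6 cells (section 4.1), so 16 per arm. Alpha is 0.05 (9.4.1). Figure 3 uses 3 groups, 2 measurements, an effect of 0.288 and correlation 0.5; the stated power is 93% (9.2). The only pairwise behavioural effect given is 0.480, from a crossover study of another task (9.2).

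**The plan's own figure.** For a within-between interaction in the G\*Power convention, λ = f²·N·m/(1−ρ), with (k−1)(m−1) and (N−k)(m−1) df. Taking 0.288 as f: λ = 0.288² × 48 × 2/0.5 = 15.9 on 2 and 45 df, and power is 94.2%, close to the stated 93%. With correlation 0.7, N = 21 gives 80.6%, matching the stated minimum of 21. So the stated power is that of the three-group omnibus interaction. (It reproduces only when the partial eta squared is entered directly as f. That is a separate matter.)

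**Set-up.** With two time points, the interaction is a one-way comparison of change scores, with 48 − 3 = 45 error df. Let d be the shift of one arm in SDs of change. At correlation 0.5 the SD of change equals the raw SD, since √(2(1−0.5)) = 1. The SHAPS covariate is ignored; it would cost one error df.

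- Omnibus: λ = 16·[(2d/3)² + 2(d/3)²] = 16·(2/3)d²; reject if F(2,45) > 3.20.
- Planned contrast: noncentrality d√(16/2) = 2.83d; critical t(45) = 2.01.
- Tukey pair: same noncentrality; critical value 2.42.

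The joint events (omnibus significant and Tukey significant) were simulated.

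**Only theta-gamma differs (delta-beta equals sham).**

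| d | Omnibus null rejected | Omnibus and Tukey show delta-beta > sham |
|---|---|---|
| 0.48 | 25% | about 1% |
| 0.8 | 61% | about 1% |
| 1.0 | 81% | about 1% |

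The omnibus rates are the same if theta-gamma falls, or if delta-beta alone falls.

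**Only delta-beta differs (a true increase): power to conclude delta-beta > sham.**

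| d | Omnibus plus Tukey | Tukey alone | Planned contrast, two-sided 5% |
|---|---|---|---|
| 0.48 | 15% | 15% | 26% |
| 0.8 | 44% | 44% | 60% |
| 1.0 | 65% | 66% | 79% |
| 1.2 | 83% | 83% | 91% |

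The first two columns barely differ, so the loss is almost all Tukey adjustment.

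**At the plan's own λ.** Setting 16·(2/3)d² = 15.9 gives d = 1.22. There the omnibus has 94% power, the planned contrast 92% and the Tukey pair 84%.

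**The case against.** The strongest reply is that the present plan would not mislead anyone about delta-beta. Section 9.4.2 states the expected driver in advance and names the follow-up. A reader who sees 81% might infer that the trial has an 81% chance of wrongly crediting delta-beta. The documents do not support that: in the same scenario Tukey shows delta-beta above sham about 1% of the time, less than the 2.5% that a planned two-sided 5% contrast allows in that direction. This part of the reply stands. What remains is that rejecting the 9.1 null is not tied to any delta-beta finding.

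Omnibus followed by Tukey is a valid procedure, and the lost power is the ordinary price of controlling error over three pairs. That also stands. It is a poor bargain only because one of the three pairs serves no stated objective, in a pilot with 16 per arm.

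A reader might also infer that the whole plan asks about placebo. Only 9.2 does. The title concerns the causal role of delta-beta coupling, for which the control frequency matters too. A delta-beta versus sham contrast alone could be positive from a non-specific stimulation effect: 79% of the time if both active arms rise by 1.0 SD. The proposed sequence therefore needs its second step.

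Finally, the two-level analysis in 9.2 already matches the objective, so it would be wrong to say that the sponsor simply chose an omnibus test. The documents hold two incompatible primary analyses.

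**Conclusion.** The point holds as a mismatch between objective and test, together with an internal contradiction. Under 9.1 and 9.4.2 the primary result can be formally positive with the objective unmet: 25% to 81% of trials if theta-gamma alone shifts change by 0.48 to 1.0 SD. It is not a raised risk of a false delta-beta claim. If delta-beta alone works, naming the contrast in advance gains about 11 to 16 percentage points of power between 0.48 and 1.0 SD, and about 8 at 1.2 SD.

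The effect sizes are assumptions. The documents give no between-arm effect on this task, and carrying 0.480 over as a between-arm difference in change is itself an assumption. At that value the planned contrast has only 26% power, so the fix does not make the trial adequately powered there. The figures also assume equal variances and 16 analysed per arm. The structural argument extends to the secondary outcome, but no size was worked out for it.

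**What to change.** Make sections 9.1, 9.2, 9.4.2 and 9.4.3 agree on one sequence:

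1. Primary test: the delta-beta minus sham difference in change, estimated from the three-arm model so that all 48 participants supply the error term, two-sided 0.05. State that success requires a significant increase; a two-sided contrast alone would not settle direction.
2. Only if that is significant, test delta-beta minus theta-gamma at 0.05 as the frequency-specificity claim. The fixed order keeps the familywise error of the two tests at 5%.
3. Report the three-arm interaction and theta-gamma versus sham descriptively, with confidence intervals.

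Replace the 93% in 9.2 with power for the named contrast over a stated range of effects, and do the same for the secondary outcome.

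The cost is analysis-plan text before unblinding, a revised power statement, and the loss of formal inference on theta-gamma versus sham, which no objective requires. Recruitment, procedures and data collection do not change.
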